Achievement of Steady State (Part B: Repeat Dose Study Phase)

Steady-state will be assessed visually by plotting trough concentration levels, C_{τ} , collected pre-morning dose versus collection day by dose. In addition, statistical analysis of trough concentration levels (e.g., Days 6,7,9, and 10 (7 day repeat dosing period) or 6-7, 16-17 (14 day repeat dosing period) will be performed after log-transformation of the concentrations. A mixed effects ANOVA model will be fit with day (continuous variable) as a fixed effect and subject as a random effect for each dose level separately. The coefficient for the slope of the day effect on the log-scale will be used to evaluate steady state for each dose. The 90% confidence intervals for the slope will be calculated.

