
Will be statistically analyzed using the power model
 $y = \alpha * \text{dose}^\beta$ 
Where y =PK parameter being analyzed and α= subject
 
Log_e transformed data will be analyzed by fitting the following terms in the mixed effect model:
 
 Fixed effect: log_e (dose) Random effect: Subject (Intercept only)
Model Checking & Diagnostics

 For the Mixed Model, model assumptions will be checked, and appropriate adjustments may be applied based on the data. Distributional assumptions underlying the model used for analysis will be examined by obtaining a normal probability plot of the residuals and a plot of the residuals versus the fitted values (i.e. checking the normality assumption and constant variance assumption of the model respectively) to gain confidence that the model assumptions are reasonable. If there are any departures from the distributional assumptions, alternative transformations, such as data squared or square root of data, will be explored.

 • Non-parametric analyses will be conducted if the normality assumption does not hold.
Model Results Presentation
Estimates of the mean slopes of \log_e (dose) will be reported along with corresponding 90% confidence intervals (slope \approx 1 implies dose proportionality)
Pharmacokinetic Statistical Analyses - Achievement of Steady State – Repeat Dose (Part B)
Endpoint / Variables
Trough plasma concentrations at the end of the dosing interval (C_{τ}) for repeat doses Days 6,7,9,10, 11, 15,16, and 17 (6, 7, 9 & 10 for reduced treatment period cohort)
Model Specification

\log_e-transformed values of the endpoint will be statistically analyzed separately by dose using Mixed Model (MM) ANOVA.
 
 • Fixed effect: day as continuous variable, dose, day*dose • Random effect: Subject 
An unstructured covariance structure for the G matrix will be used.
 
 • In the event that this model fails to converge, alternative covariance structures may be considered. • Akaike's Information Criteria (AIC) will be used to assist with the selection of covariance structure. 
Analyses will be done with the MIXED Procedure in SAS, using the Kenward-Roger option to estimate denominator degrees of freedom and standard errors

Model Checking & Diagnostics

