
 • For the Mixed Model, model assumptions will be checked, and appropriate adjustments may be applied based on the data. • Distributional assumptions underlying the model used for analysis will be examined by obtaining a normal probability plot of the residuals and a plot of the residuals versus the fitted values (i.e. checking the normality assumption and constant variance assumption of the model respectively) to gain confidence that the model assumptions are reasonable. • If there are any departures from the distributional assumptions, alternative transformations, such as data squared or square root of data, will be explored. • Non-parametric analyses will be conducted if the normality assumption does not hold.
Model Results Presentation

The coefficient for the slope of the day effect on the log-scale will be used to evaluate steady state for each dose. The 90% confidence intervals for the slope will be calculated.
 
Steady-state will be assessed visually by plotting trough concentration levels, C_{τ}, collected pre-morning dose versus collection day by dose.

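### The steady-state trough model names no random day slope, so its per-dose 90% CI is too narrow if participants' slopes differ; its dose terms also conflict with a per-dose fit

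*SAP*

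**What the plan says.** SAP 8.2.4.1.2, Achievement of Steady State, takes pre-dose concentrations on Days 6, 7, 9, 10, 11, 15, 16 and 17 (Days 6, 7, 9 and 10 in the reduced-treatment cohort). The log-transformed "values of the endpoint will be statistically analyzed separately by dose using Mixed Model (MM) ANOVA". The model terms are "Fixed effect: day as continuous variable, dose, day*dose" and "Random effect: Subject". It adds: "An unstructured covariance structure for the G matrix will be used". AIC assists the choice of covariance structure, and Kenward-Roger supplies standard errors and degrees of freedom. For reporting: "The coefficient for the slope of the day effect on the log-scale will be used to evaluate steady state for each dose", with a 90% CI and a plot of troughs by day.

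Protocol 9.4 describes a simpler model, with "day (continuous variable) as a fixed effect and subject as a random effect for each dose level separately". It has no dose terms. SAP Table 1, which records changes from the protocol analysis, lists only changes to analysis populations.

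**The concern.** There are two separate problems.

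**Specification.** Within one dose, dose is constant and day*dose is a multiple of day, so neither term can be estimated. A programmer must either drop them or ignore the instruction to fit by dose. The SAP does not say which.

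**Random effects.** No participant-specific day slope is named. If the subject effect is a random intercept, all departures from a common slope go into the residual, including systematic differences between participants in how their troughs drift. The slope's standard error is then computed as if the troughs carried independent information about drift, on 62 residual degrees of freedom in a 14-day cohort, although only 9 participants inform it. If slopes really differ, the interval is too short. It may then suggest a drift that is not there, or appear to rule out a drift that the data cannot rule out.

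**Working it through.** **Inputs from the documents.** n = 9 active participants per Part B cohort (Protocol 9.2). The trough days are those in SAP 8.2.4.1.2, and the nominal level is 90%. The half-life is about 13 h (SAP 13.4.1). Repeat dosing starts on Day 4 (Protocol 4.1).

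**Inputs assumed.** The documents give neither the within-participant residual SD of log troughs (σ) nor the between-participant SD of the log-trough slope (τ). I took σ = 0.15–0.20 and varied τ.

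**Step 1: the dose terms.** In a single-dose fit, the design matrix (intercept, day, dose, day*dose) has rank 2 of 4. The dose terms drop out, and the day slope and its CI are those of the protocol's model.

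**Step 2: design constants.** Sxx is the sum of squares of day about its mean.
- 14-day: 1157 − 91²/8 = 121.875; residual df = 9×8 − 9 − 1 = 62.
- 7-day: 266 − 32²/4 = 10; residual df = 9×4 − 9 − 1 = 26.

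**Step 3: standard errors for a separate fit.**
- True variance of the mean slope: (τ² + σ²/Sxx)/n.
- Variance that the random-intercept model reports, on average: (σ² + τ²·Sxx·(n−1)/df)/(n·Sxx).

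Example, 14-day, τ = 0.02, σ = 0.15:
- True SE = √[(0.0004 + 0.0225/121.875)/9] = 0.0081.
- Model SE = √[(0.0225 + 0.0004×121.875×8/62)/(9×121.875)] = 0.0051.
- The SE is understated by a factor of about 1.6. With σ = 0.20 the factor is about 1.4.

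**Step 4: coverage of the nominal 90% CI.** By simulation, n = 9, separate fits. The range is over σ = 0.15–0.20.

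| Schedule | Slope SD per day | Random intercept | t-interval on participants' slopes |
|---|---|---|---|
| 14-day | 0 | 90% | 90% |
| 14-day | 0.004 | about 89% | 90% |
| 14-day | 0.01 | 83–86% | 90% |
| 14-day | 0.02 | 70–77% | 90% |
| 7-day | 0 | 90% | 90% |
| 7-day | 0.05 | 81–84% | 90% |

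The nominal level is therefore reproduced when slopes are common, and is lost as they diverge.

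**Step 5: which τ is plausible?** One source of differing slopes is incomplete accumulation at the first trough. With once-daily dosing, one compartment and a 13 h half-life, the Day 6 trough is 1 − 2^(−48/13) = 92% of plateau and the Day 9 trough is 1 − 2^(−120/13) = 99.8%. Letting half-life vary with an assumed 30% CV gives a slope SD of about 0.004/day on the 14-day schedule, hence about 89% coverage. In the 7-day cohort the same mechanism also leaves about 89%.

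**Step 6: a pooled fit instead.** With three doses, day*dose and one common residual variance (df = 62 + 62 + 26 = 150), I varied τ/σ from 0.05 to 0.5 per day. The 14-day cohorts have coverage close to the separate fits (76% at a ratio of 0.1, against 77%). The 7-day cohort has 90–92%, so its CI is not too narrow.

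**Step 7: cost of the alternative.** When τ = 0, the participant-slope interval is wider by about 1.8595×0.969/1.6698 = 1.08 in a 14-day cohort and by about 1.07 in the 7-day cohort. The constants are the t quantiles on 8 and 62 df; 0.969 is the small-sample factor for an SD on 8 df.

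**The case against.** **The random effects may not be intercept-only.** The SAP writes an intercept-only restriction for its power models but not here, and it asks for an unstructured G matrix, which has content only with a second random effect. This stands to the extent that the model is under-specified rather than explicitly wrong. The G-matrix sentence does not settle it, because it also follows the food-effect ANOVA, where the random effect is again just Subject.

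**A reader might infer that the dose terms make the CI too narrow, or that only a reference dose's slope will be reported.** Neither follows. Aliased terms change nothing, and the SAP asks for a slope for each dose; example shell PK_T6 has one row per treatment.

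**The trough slope is not the only evidence on steady state.** Protocol 9.4 also bases attainment of steady state on the AUC ratio Rss, with its own 90% CI, and troughs are plotted. There is no formal hypothesis and no drift threshold. This stands, and it lowers the stakes.

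**The large coverage losses rest on assumed slope SDs.** This stands too. At the SAP's own half-life, accumulation alone costs about one percentage point. Larger losses need another source of drift, such as clearance that changes over time in some participants, or a longer half-life; the documents quantify neither.

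**Existing safeguards.** Kenward-Roger corrects small-sample bias under the fitted covariance; it does not add an omitted slope variance. The listed checks (normal plot, residuals against fitted values) are not aimed at slope heterogeneity, although the SAP does allow adjustments after model checking.

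**Conclusion.** The specification conflict is certain, but it is a matter of wording: it leaves the programmer an unrecorded choice and does not by itself bias the slope. The random-effects point holds conditionally. On the natural random-intercept reading, the per-dose CI falls short of 90% coverage if participants' trough slopes differ. In the 14-day cohorts the shortfall runs from about 1 point (slope SD 0.004/day) through 4–7 points (0.01/day) to 13–20 points (0.02/day), for an assumed residual SD of 0.15–0.20. For the 7-day cohort fitted separately, the loss is small unless the slope SD reaches about 0.05/day; in a pooled fit there is none.

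The documents do not support reading the 70–77% figure as the expected performance, or saying that every dose's CI is too narrow. This is a cheap improvement to a secondary estimation analysis, of modest priority.

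**What to change.** Amend SAP 8.2.4.1.2 (Achievement of Steady State) as follows:

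1. Fit each dose separately with day as the only fixed effect, as in Protocol 9.4, and delete dose and day*dose.
2. Preferably, estimate each participant's own log-trough slope by least squares, and report the mean per dose with a 90% t-interval on n−1 df. This is the version whose coverage was checked above.
3. Alternatively, name a random intercept and a random day slope per subject with an unstructured G matrix, and state the fallback for non-convergence or a zero slope variance. Reverting to intercept-only after seeing the data was not tested here and could itself affect coverage with 9 participants and 4 troughs.

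The cost is a few lines of SAP text and a small programming change. The CI is about 7–8% wider if slopes do not differ. No extra samples or participants are needed.

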8.2.4.1.3. Statistical Methodology Specification for Part C

Pharmacokinetic Statistical Analyses - Food Effect -Single Dose (Part C)
Endpoint / Variables
AUC(0-t), AUC(0-∞), Cmax and t1/2
Model Specification

Log_e-transformed values of AUC(0-t) and AUC(0-∞) and actual value of t1/2 will be statistically analyzed using Mixed Model (MM) ANOVA.
 
 • Fixed effect: period, treatment(fed/fasted) • Random effect: Subject 
An unstructured covariance structure for the G matrix will be used.
 
 • If this model fails to converge, alternative covariance structures may be considered. • Akaike's Information Criteria (AIC) will be used to assist with the selection of covariance structure. 
Analyses will be done with the MIXED Procedure in SAS, using the Kenward-Roger option to estimate denominator degrees of freedom and standard errors

Model Checking & Diagnostics

 • For the Mixed Model, model assumptions will be checked, and appropriate adjustments may be applied based on the data. • Distributional assumptions underlying the model used for analysis will be examined by obtaining a normal probability plot of the residuals and a plot of the residuals versus the fitted values (i.e. checking the normality assumption and constant variance assumption of the model respectively) to gain confidence that the model assumptions are reasonable. • If there are any departures from the distributional assumptions, alternative transformations, such as data squared or square root of data, will be explored. • Non-parametric analyses will be conducted if the normality assumption does not hold.
Model Results Presentation
Point estimates for the differences in means (GSK3439171A fed – GSK3439171A fasted) and corresponding 90% CIs will be constructed from the least squares means, using the residual variance. These will then be back-transformed to provide point estimates and corresponding 90% CIs for the ratio of geometric means fed:fasted.
Endpoint(s)
Tmax Note: This endpoint will not be log transformed for analysis
Model Specification
Wilcoxon matched pair test
Model Results Presentation
Point estimate and 90% confidence interval for the median difference (fed – fasted)

Note: AUC(0-t) is only reported when AUC(0-∞) is not reportable Population

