A statistical analysis will be performed for each parameter separately using the power model with the log-transformed PK parameter as the dependent variable and log(dose) as a fixed effect. For Part A, the intercept and slope will be fit as random effects. In addition, effects for cohort and cohort by log(dose) may be included in the model to examine differences in slopes across cohorts. Estimates of the slopes will be reported along with corresponding 90% CIs (slope \approx 1 implies dose proportionality).

Food Effect (Part C: Single Dose Study)

The effect of food on the PK of GSK3439171A (AUC(0-inf), Cmax, and $t_{1/2}$) will be examined. An analysis of variance model will be fitted separately to each of the log-transformed PK parameters with period and treatment (fed or fasted) as fixed effects and participant as a random effect. Point estimates for the differences in means (GSK3439171A fed – GSK3439171A fasted) and corresponding 90% CIs will be constructed from the least squares means, using the residual variance. These will then be back-transformed to provide point estimates and corresponding 90% CIs for the ratio of geometric means fed:fasted.

Accumulation (Part B: Repeat Dose Study Phase)

The extent of accumulation of GSK3439171A will be based on AUC (Ro) and Cmax (RCmax).

Statistical analysis of log-transformed AUC(0- τ) and Cmax will be performed separately and by dose using an ANOVA model with a fixed, categorical effect for day and a random effect for participant. The accumulation ratios (Ro and RCmax) of

GSK3439171A will be evaluated for each dose by exponentiating the difference in least squares means (Day 13 or 17 – Day 1) and the associated 90% CI.

Time Invariance

Assessment of the achievement of steady state will be based on the AUC (Rss). The time invariance ratio will be calculated as the ratio of AUC(0- τ) on Day 13 or 17 over AUC(0-inf) on Day 1. The time invariance ratio will be listed and summarized along with other PK parameters.

Statistical analysis of the log-transformed AUCs will be performed separately for each dose using an ANOVA model with a fixed, categorical effect for day and a random effect for participant. The time invariance ratio of GSK3439171A will be evaluated for each dose by exponentiating the difference in least squares means (Day 17 – Day 1) and the associated 90% CI. The values of AUC used in the analysis will be AUC(0-inf) on Day 1 and AUC(0- τ) on Day 13 or 17.

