13.12.7. Pharmacokinetic Tables

Pharmacokinetic: Tables					
No.	Population	IDSL / Example Shell	Title	Programming Notes	Deliverable [Priority]
PK concentration					
4.1.	PK	PK01	Summary of Plasma GSK3439171 Pharmacokinetic Concentration-Time Data (ng/mL) – Part A		SAC
4.2.	PK	PK01	Summary of Plasma GSK3439171 Pharmacokinetic Concentration-Time Data (ng/mL) – Part B		SAC
4.3.	PK	PK01	Summary of Plasma GSK3439171 Pharmacokinetic Concentration-Time Data (ng/mL) – Part C		SAC
PK Urine					
4.4.	PK	PK02	Summary of Pharmacokinetic Urine Excretion Rate-Time Data – Part B		SAC
PK derived parameters					
4.5.	PK	PK03	Summary Statistics of Derived Plasma GSK3439171 Pharmacokinetic Parameters – Part A		SAC
4.6.	PK	PK03	Summary Statistics of Derived Plasma GSK3439171 Pharmacokinetic Parameters – Part B		SAC
4.7.	PK	PK03	Summary Statistics of Derived Plasma GSK3439171 Pharmacokinetic Parameters – Part C		SAC
4.8.	PK	PK05	Summary Statistics of Log-Transformed Derived Plasma GSK3439171 Pharmacokinetic Parameters – Part A		SAC
4.9.	PK	PK05	Summary Statistics of Log-Transformed Derived Plasma GSK3439171 Pharmacokinetic Parameters – Part B		SAC

Pharmacokinetic: Tables					
No.	Population	IDSL / Example Shell	Title	Programming Notes	Deliverable [Priority]
4.10.	PK	PK05	Summary Statistics of Log-Transformed Derived Plasma GSK3439171 Pharmacokinetic Parameters – Part C		SAC
4.11.	PK	PK_T1	Statistical Analysis of Plasma GSK3439171 Pharmacokinetic Parameters: Analysis of Variance (ANOVA) – Part A	t1/2	SAC
4.12.	PK	PK_T1	Statistical Analysis of Plasma GSK3439171 Pharmacokinetic Parameters: Analysis of Variance (ANOVA) – Part B	t1/2 Include 'Visit' as first column	SAC
4.13.	PK	PK_T1	Statistical Analysis of Plasma GSK3439171 Pharmacokinetic Parameters: Analysis of Variance (ANOVA) – Part C	t1/2	SAC
4.14.	PK	PK_T2	Statistical Analysis of Log-Transformed Plasma GSK3439171 Pharmacokinetic Parameters: Analysis of Variance (ANOVA) – Part A	AUC(0-t), AUC(0-24), AUC(0-∞), Cmax, Cτ, AUC(Rp)	SAC
4.15.	PK	PK_T2	Statistical Analysis of Log-Transformed Plasma GSK3439171 Pharmacokinetic Parameters: Analysis of Variance (ANOVA) – Part B	AUC(0- τ), AUC(0-∞), Cmax, Cτ Include 'Visit' as first column	SAC
4.16.	PK	PK_T2	Statistical Analysis of Log-Transformed Plasma GSK3439171 Pharmacokinetic Parameters: Analysis of Variance (ANOVA) – Part C	AUC(0-t), AUC(0-∞), Cmax	SAC

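### The Part C food-effect rule back-transforms a half-life contrast that was never log-transformed, and SAP Table 1 does not record the change of scale from the protocol

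*SAP*

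**What the plan says.** The Part C box in SAP 8.2.4.1.3 names four endpoints for the mixed model: "AUC(0-t), AUC(0-∞), Cmax and t1/2". The model specification gives a log scale to AUC(0-t) and AUC(0-inf). It then says that the "actual value of t1/2 will be statistically analyzed using Mixed Model (MM) ANOVA". Cmax is not mentioned in that sentence. The results rule starts from "Point estimates for the differences in means (GSK3439171A fed – GSK3439171A fasted) and corresponding 90% CIs" and continues: "These will then be back-transformed to provide point estimates and corresponding 90% CIs for the ratio of geometric means fed:fasted". tmax is handled separately, by a Wilcoxon matched-pair analysis reported as a median difference.

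Protocol 9.4 names AUC(0-inf), Cmax and t1/2 for the food effect and has one model, "fitted separately to each of the log-transformed PK parameters with period and treatment (fed or fasted) as fixed effects". There t1/2 is on the log scale, and the same back-transformation is valid.

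SAP Table 1, which is meant to list changes from the protocol's analysis, contains only changes to analysis populations.

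In SAP 13.12.7, the Part C model results go to Table 4.13 (t1/2, shell PK_T1) and Table 4.16 (the AUCs and Cmax, shell PK_T2). Table 4.16 is titled "Statistical Analysis of Log-Transformed Plasma GSK3439171 Pharmacokinetic Parameters: Analysis of Variance (ANOVA) – Part C".

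**The concern.** The SAP changed the scale of t1/2 but kept a results rule that works only on the log scale. Followed as written, the rule gives a t1/2 figure labelled as a fed:fasted ratio that is not one. If the programmer declines to exponentiate hours, the plan does not say what is reported for t1/2 instead.

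Food effect is a secondary objective and the purpose of Part C, and t1/2 is one of its stated parameters. The change of scale is also a departure from the protocol that a reader of Table 1 would not find.

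**Working it through.** The plan gives no figure to reproduce here. The check is a reconciliation of the text, followed by an illustration of size.

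**1. Scale by parameter**

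| Parameter | Protocol 9.4 | SAP 8.2.4.1.3 model sentence | Rest of SAP |
|---|---|---|---|
| AUC(0-inf) | log | log | log (Table 4.16) |
| AUC(0-t) | not in the food-effect model | log | log (Table 4.16) |
| Cmax | log | not named | log (note on Table 4.16; absent from the untransformed list in 13.5.3) |
| t1/2 | log | actual value | untransformed (13.5.3; Table 4.13) |

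Only t1/2 has a real conflict between the two documents. For Cmax the gap is one missing word.

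**2. What the results rule does to t1/2**

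On the log scale, exp(mean log fed − mean log fasted) is a ratio of geometric means. On the raw scale, exp(mean fed − mean fasted) is the exponential of a number of hours. Take a fasted half-life of 13 h (SAP 13.4.1) and assumed differences d, which are not in the documents:

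| d (h) | True ratio (13 + d)/13 | exp(d) |
|---|---|---|
| −1 | 0.92 | 0.37 |
| +0.5 | 1.04 | 1.65 |
| +1 | 1.08 | 2.72 |
| +1.3 | 1.10 | 3.67 |
| +2 | 1.15 | 7.39 |

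The result also depends on the unit. With time in days, +1 h gives exp(1/24) = 1.04 where hours give 2.72. The direction of effect survives, because exp(d) exceeds 1 exactly when d is positive. The magnitude and the interval have no meaning as a ratio.

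**3. Simulation**

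This used 5,000 runs of 12 paired participants, with an assumed true ratio of 1.10, within-participant CV of 20% and between-participant CV of 30%. None of these three values is in the documents. The log-scale estimate had a median of 1.10. The exponentiated raw difference had a median of 3.92, with 5th to 95th percentiles of 0.54 to 31.7.

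**4. Comparison with Part B**

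SAP 8.2.4.1.2 also analyses t1/2 untransformed, but it limits exponentiated ratios to AUC(0-τ), Cmax and the AUC used for Rss. Part C has no such limit.

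**5. Where the ratio would appear**

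The Part C tables in 13.12.7 for concentrations and PK parameters are 4.3, 4.7, 4.10, 4.13 and 4.16 (4.23 and 4.26 concern genetic consent). Shells PK_T1 and PK_T2 have columns for per-treatment LS mean, 95% CI and within-participant CV, with no contrast. The only shell with a ratio and a 90% CI is PK_T5, which serves Part B Table 4.17. The interval level differs as well. With 12 participants in two periods the residual degrees of freedom are 24 − 12 − 1 − 1 = 10, so a 95% interval is 2.228/1.812 = 1.23 times as wide as the 90% interval that the text specifies.

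**The case against.** The best defence is that untransformed t1/2 is a consistent SAP convention, found in the Part A, B and C boxes and in 13.5.3. The table list separates t1/2 (Table 4.13, arithmetic LS means) from the log-scale parameters (Table 4.16, geometric LS means). Only a transformed variable can be back-transformed, so a sensible reader would apply the ratio sentence to the AUCs and Cmax alone. The protocol also leaves statistical detail to the analysis plan, and no hypothesis is tested. Much of this stands: an experienced programmer would probably not exponentiate hours, so 3.67 shows what the written rule produces and does not forecast an error. But the rule has no exception for t1/2, Part B shows that the authors could write one, and the change from the protocol remains unrecorded.

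A reader might also infer two stronger points that the documents do not support.

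- **That Cmax is analysed untransformed, or that its scale is left to the programmer.** The box only omits it from one sentence. The note on Table 4.16, the list in 13.5.3 and protocol 9.4 all put it on the log scale.
- **That the food-effect estimate has no planned output.** The results rule itself requires the ratio with a 90% CI. SAP 5.1 lists a fasted-versus-fed comparison for display. The shells are labelled as examples that are not study specific, and raw SAS Listings 121 and 124 could hold the contrasts. What stands is narrower: no listed Part C table is assigned the contrast, and 5.1 names it in the opposite order to the fed:fasted ratio.

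**Conclusion.** The t1/2 point holds. SAP 8.2.4.1.3 combines an untransformed analysis with a back-transformation that suits only log-scale contrasts. It departs from protocol 9.4 in doing so, and SAP Table 1 is silent. That finding rests on the text alone. The size shown (3.67 against 1.10) rests on the 13 h half-life and an assumed 10% effect; other effects give other wrong values.

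The consequence is confined to t1/2. The AUC and Cmax food-effect ratios, which carry the main exposure conclusion, remain sound. The missing mention of Cmax and the unassigned display are minor drafting gaps.

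**What to change.** Choose one scale for t1/2 in the Part C box.

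- **Log scale, as in protocol 9.4.** The back-transformation rule then stands. Move t1/2 from Table 4.13 to Table 4.16 and note the exception in 13.5.3.
- **Hours.** Report the fed minus fasted difference with a 90% CI, and limit back-transformation to AUC(0-t), AUC(0-inf) and Cmax. This matches the rest of the SAP.

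Record the decision in SAP Table 1; the second option is a departure from the protocol and needs its reason stated.

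As minor corrections, add Cmax to the log-transformed list in the box. Assign the fed:fasted ratio with its 90% CI to a listed Part C table, either a new one modelled on PK_T5 or a programming note on Table 4.16. If t1/2 stays in hours, give its difference and 90% CI a place too, for example by a note on Table 4.13.

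The cost is a few lines of SAP text and at most one extra table. Design, conduct and data collection do not change.
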